Our study hypothesis is that the proportion of children seroconverting after MR vaccine dose at 9 months following administration of an earlier MR vaccine dose at 6 months of age (Arm A) is not different compared with the immunogenicity obtained when MR vaccine dose is administered at 9 months to infants who have had no previous dose of MR vaccine (Arm B). A secondary hypothesis is the incidence and spectrum of adverse reactions following immunization will be similar between doses given at 6 and 9 months (Arm A), and at 9 months.

The following questions are to be answered by the study:

1. What is immunogenicity of MR vaccine at 6 months of age?
2. What is the impact of the 6-month MR dose on immunogenicity of the 9-month MR dose?
3. What are the frequency and severity of adverse reactions following MR vaccination at 6 months and 9 months?
4. What is correlation between the measles and rubella antibody levels in mothers and level of maternal antibodies in infants

Specific Objectives

Primary objectives

1. To assess immunogenicity of MR vaccine at 6 months of age
2. To assess immunogenicity of MR vaccine at 9 months of age among children without prior measles and rubella vaccination, compared with MR vaccine immunogenicity among those who had a prior MR vaccination at 6 months of age

Secondary objectives:

1. To assess the frequency of adverse reactions following administration of MR vaccine at 6 months
2. To compare the immunogenicity of the MR vaccine first dose administered at 6 months vs at 9 months.
3. To assess the proportion of mothers with undetectable, detectable and protective levels of measles and rubella antibodies

4. To determine the extent of variation in measles antibodies in a convenience sample of women of child bearing age in a population with a long standing measles vaccination program
5. To determine the extent of variation in rubella antibodies in a convenience sample of women of child bearing age in a population where rubella vaccine have been recently introduced
6. To determine if variation in antibody levels in infants at 6 months is predominately explained by variation in starting antibody levels in the mother in this population
7. To estimate the half-life of decay of measles and rubella antibodies in infants

Background

Measles

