2. A study doctor will obtain a medical history and conduct a medical examination to assess whether the infant is eligible to take part in the study.
3. Infants who are not eligible per inclusion and exclusion criteria will be excused from study participation and it will be documented in the case reporting form.

4. Participants who meet temporary exclusion criteria at enrollment will be excused for the day and will be requested to return several days later, but as long as their age is 180 days, +/- 7 days. A note will be made in the case reporting form.
5. The eligible infant will be given a study ID and assigned to a study arm (arm A or B) according to a pre-determined randomization scheme. Further details of the randomization scheme are described in the 'Data Analysis' section.
6. Parents will be interviewed and socio-demographic and clinical information will be collected as per standardized study questionnaire.
7. One blood specimen (minimum of 1 ml) will be collected by venipuncture from all enrolled infants following the enrollment. During visits in which the child receives vaccine, blood samples will be drawn before vaccine administration.
8. One blood specimen (1 ml) will be collected by venipuncture from mothers of all enrolled infants following the enrollment.
9. Infants randomized to the study arm A will be administered the first dose of MR vaccine. Vaccine will be administered only if an adequate blood specimen has been collected from the participant.
10. The participant will be observed for 30 minutes for any adverse reactions from administration of the vaccine or the blood collection.
11. A research assistant will schedule the second visit. All participants will be requested to return 3 months later after enrolment, i.e., at 9 months of age.

Follow up home visit (2 days after MR vaccination). Safety monitoring.

- Children in study arm A, who received a 6 month dose of MR vaccine, will be visited by a field research assistant at their homes 2 days after MR vaccination. This visit is to identify if any participants experienced any adverse events following immunization.
- The research assistant will inquire about and record any potential adverse events after the 6 month dose of MR. All finding will be captured in the AEFI form.

Study site visit at 9 months of age. Blood draw and MR vaccination.

During the 9 month visit, the following procedures will be conducted:

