1. The study physician will complete the study questionnaire and examine the participant
2. 1 ml of blood will be drawn from each infant (both study arms A and B).
3. Study vaccine will be administered to ALL infants (both study arm A and B). The participant will be observed for 30 minutes to monitor for any adverse reactions
4. Schedule the next visit at 11 months of age

MR vaccination at 9 months is now routinely given in Bangladesh. Therefore, there will be no follow-up household safety monitoring visit after the 9 month MR dose during the study.

Temporary exclusion

- Participants who meet temporary exclusion criteria for vaccination will be excused for the day and will be requested to return several days later, but as long as their age is 9 months, +/- 7 days. A note will be made in the study log book.

Study site visit at 11 months of age. Blood draw and Study exit.

This visit will be the third and last planned study visit for participants. During this visit, the following procedures will be conducted:

1. The study physician will complete the follow up form and examine the participant
2. 1 ml of blood will be drawn from each infant (from both study arms A and B).
3. At study exit, parents will be reminded to bring their child to the fixed site clinic or another EPI facility to receive their second dose of measles vaccine according to the new EPI schedule (at age 15 months).

Laboratory evaluations

Clinical Laboratory Evaluations

No clinical laboratory evaluations will be offered in this study. Laboratory assays described in the protocol are for research purposes only and laboratory results will not be used for clinical diagnosis.

Special Assays or Procedures

Blood samples will be obtained at 6 months from all infants (at enrolment) and mothers and tested for measles and rubella antibodies. The baseline levels will identify infants who have transplacentally transferred maternal antibodies been exposed to natural measles infection before the enrolment to the study. The mothers' antibody levels will be determined and they will be classified as "susceptible" or "protected" (seroprotection definitions will be the same: titer of ≥ 120 mIU/mL for measles and rubella >10 mIU/mL).

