- Compare the proportion of participants demonstrating seroconversion at 9 months in both study arms. We will use chi-square test to test for statistical significance
- Compare the change in median titers of measles and rubella antibodies by study arm
- Compare immunogenicity of MR vaccine administered at 6 months (Arm A) vs 9 months (Arm B). Analyse the relationship of infants' immunogenicity to MR vaccine and mothers' level of antibodies
- Analyse the relationship between the levels of infants' maternal measles and rubella antibodies and mothers' antibodies
- Analyse results of adverse events by study arm and compare by age and arm of the study.

Data Safety Monitoring Plan (DSMP)

Records to be kept

Participant data will be collected using case report forms (CRFs). Personal identifiers will not be recorded on any CRFs, biological specimens or electronic records. Participants will be identified by a participant identification number (PID), which will be provided after enrolment and randomization. The PID will be used to link information recorded in CRFs and results from laboratory analysis of biological specimens.

Data entry, cleaning and storage

Records of participants will be kept in a locked cabinet with access restricted to study staff and investigators. All computer records will be kept in a locked room. The computers will be password protected. Only the study staff and investigators will be authorized to access the digital records.

Data from the CRFs will be entered into an electronic database. Checks will be performed to identify and correct data entry errors. After the completion of analysis and publication of study results, the study forms and database will be archived. The forms will be stored in a locked cabinet with access restricted to investigators. The database will be password protected.

Site monitoring plan

Prior to start of the study, Standard Operating Procedures (SOPs) will be developed by investigators in consultation with study staff. Study staff will be trained in study procedures and human subjects' management. After start of the study monitoring of study site will be conducted twice.

During these monitoring visits the following study documents and procedures would be reviewed:

1. Participant records, including consent forms
2. CRFs and other supporting data
3. Adverse event forms
4. Data Safety and Monitoring Board (DSMB) reports
5. Laboratory specimen records
6. Vaccine and biological materials storage and records

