All participants will be observed for 30 minutes post vaccination to monitor for any immediate adverse reactions to the vaccine. Properly skilled medical personnel will be immediately available in case of an emergency in the event of an unexpected adverse reaction. The study physician will record at the end of this period the presence of any potential reaction to the vaccine. At the end of each study visit, the physician or study coordinator will provide the parents with a phone number for a study nurse to call if they have any questions or experience any reactions to the vaccine.

A study staff will visit the house of the participant to inquire and record any potential adverse event in 48 hours after the first dose of MR administered at 6 months (study arm A).

Should a serious illness occur while enrolled in the study (requiring a physician's visit or hospitalization), parents will be instructed to seek medical care immediately. Medical care for expected

minor illnesses that will develop during the follow up period in study participants such as rash, fever or respiratory infections as well as any adverse outcomes of the vaccination judged to be possibly, probably or definitely related (detailed below) to study vaccines or vaccination will be provided free of charge.

Recording, monitoring and reporting of adverse events

During each study visit the study staff will question the parents of the participant about possible adverse events (AE) since the previous study visit and record this in the CRF. Reported AE will be recorded in the AE form. The AE form will include a description of the event, time of onset, assessment of severity, relationship to study product, and time of resolution/stabilization of the event.

Reports of AE will be periodically discussed by the team of investigators. The study team will review the potential relationship and classify the relationship into:

1. Unable to judge
2. Not related
3. Probably not related
4. Possibly related
5. Probably related
6. Definitely related

Interpretation of vaccine-relationship to AE will be based on the type of event, the relationship of the event to the time of vaccine administration, the known biology of the vaccine and the investigators' medical judgment.

An AE will be considered a serious adverse event if it meets any of the following criteria:

1. Death during the study period
2. Hospitalization
3. Anaphylaxis associated with vaccine administration

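### Only the 6-month dose in Arm A has active 2-day follow-up, so comparing early non-serious adverse events by age, or all-source totals by arm, confounds reactions with ascertainment

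*Combined protocol and SAP*

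**What the plan says.** Under Hypothesis to be tested, the secondary hypothesis reads in its main part: "incidence and spectrum of adverse reactions following immunization will be similar between doses given at 6 and 9 months (Arm A), and at 9 months". Its counterpart under Specific Objectives is narrower and has no comparator: "To assess the frequency of adverse reactions following administration of MR vaccine at 6 months". The list of planned analyses at the end of Data Analysis adds the comparison: "Analyse results of adverse events by study arm and compare by age and arm of the study". It names no event source, time window, endpoint or test.

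Follow-up differs by dose:

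- **6-month dose, Arm A.** The section on the follow-up home visit says that these children "will be visited by a field research assistant at their homes 2 days after MR vaccination", with findings entered on an AEFI form. It provides no such visit for Arm B.
- **9-month dose, both arms.** The 9-month visit section explains that this dose is already routine and concludes: "Therefore, there will be no follow-up household safety monitoring visit after the 9 month MR dose during the study".
- **Outcome definition.** Secondary outcomes defines a 48-hour adverse event outcome for the 6-month dose only.

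Other routes are common to both arms. Every vaccinated child is observed for 30 minutes. At each visit "study staff will question the parents of the participant about possible adverse events (AE) since the previous study visit". Parents are given a nurse's telephone number, and serious adverse events are collected throughout the study.

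**The concern.** There are three dose occasions: Arm A at 6 months, Arm A at 9 months and Arm B at 9 months. The hypothesis treats them as comparable, but only the first has someone calling at the home 2 days later to ask. After the other two, a mild early event such as a local reaction or brief fever reaches the database only if a parent telephones, seeks care, or remembers it about 8 weeks later at the 11-month visit. A difference in recorded early events can then arise from the method of looking, and a real difference can be hidden by it.

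The safety of the 6-month dose is what a reader planning outbreak vaccination would take from this trial, because the 9-month dose is already in routine use. The text on possible limitations does not mention the unequal follow-up.

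**Working it through.** **Which comparisons are affected**

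| Event type | 6-month dose, Arm A | 6-month visit, Arm B (no vaccine) | 9-month dose, Arms A and B |
|---|---|---|---|
| First 30 minutes | observed | no dose given | observed |
| Non-serious, first 48 hours | home visit, telephone, recall at 9 months | recall at 9 months | telephone, recall at 11 months |
| Non-serious, later | telephone, recall over about 12 weeks | recall over about 12 weeks | telephone, recall over about 8 weeks |
| Serious | whole study | whole study | whole study |

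Only the second row depends on the home visit. Two contrasts use it: 6- versus 9-month dose for early non-serious events, and any Arm A versus Arm B total that counts home-visit events. Arm A's second dose and Arm B's first dose, both at 9 months, are followed identically.

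**Fever and rash**

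The Safety monitoring section expects high fever in 5% to 15% of recipients on days 7 to 12, and rash in about 5% starting on days 7 to 10. Both fall after a day-2 visit, so both doses rely on later reporting. Recall spans about 12 weeks for the 6-month dose and about 8 weeks for the 9-month dose, so the direction of any bias for these events is not established.

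**Size, for early events only**

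The documents give no figure for the safety comparison and no early reaction or capture rate, so there is no stated figure to reproduce. The group size of 279 per arm comes from the sample size section. All rates below are assumptions.

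- Recorded rate = true rate × capture probability.
- z = (r1 − r2) / √(2 × m × (1 − m) / 279), where m is the mean of the two recorded rates.

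Take a true rate of 10% after both doses and 90% capture with the home visit, so r1 = 0.10 × 0.90 = 9%.

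- **30% capture without the visit:** r2 = 3%, m = 0.06, standard error = √(2 × 0.06 × 0.94 / 279) = 0.0201, z = 0.06 / 0.0201 = 2.98, p about 0.003, spurious ratio 3.0.
- **60% capture:** r2 = 6%, m = 0.075, standard error = √(2 × 0.075 × 0.925 / 279) = 0.0223, z = 0.03 / 0.0223 = 1.35, p about 0.18, ratio 1.5.

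The chance of declaring a difference at two-sided 5% when none exists, by the normal approximation, is:

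| Capture without home visit | 70% | 50% | 30% |
|---|---|---|---|
| Recorded rates | 9% vs 7% | 9% vs 5% | 9% vs 3% |
| Apparent ratio | 1.29 | 1.80 | 3.00 |
| Probability of a false difference | 14% | 46% | 85% |

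The reverse error is also possible. With true rates of 10% at 6 months and 20% at 9 months, captured at 90% and 45%, both appear as 9% (0.10 × 0.90 = 0.20 × 0.45 = 0.09).

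These two-sample figures suit Arm A's 6-month dose against Arm B's 9-month dose. The comparison within Arm A is paired, so the p-values would differ but the direction would not.

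**The case against.** The strongest defence is that the plan never says to pool sources. Secondary outcomes already separates 30-minute reactions, 48-hour events and serious adverse events, and it ties the 48-hour category to the 6-month dose. Home-visit findings have their own form. The listed objective is only the frequency of reactions after the 6-month dose, which remains estimable. The 9-month home visit was left out for a stated reason, and several comparisons are fair as planned.

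All of this stands, and it limits the point. It does not remove it: the hypothesis and the planned analysis both go beyond the listed objective, and neither is confined to events collected alike.

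A reader might infer three stronger things that the documents do not support:

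- **That the safety hypothesis cannot be tested at all.** Immediate reactions, serious events and the 9-month contrast between arms can be compared on equal terms.
- **That all non-serious events are biased against the 6-month dose.** The day-2 visit precedes the expected fever and rash, and the longer recall after the 6-month dose could push the other way.
- **That events after the 9-month dose are known only from recall at 11 months.** The telephone line, free care for minor illness and collection of serious events apply after that dose too, although these routes are passive.

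**Conclusion.** The point holds in a limited form. The 6- versus 9-month comparison of non-serious events in the first 48 hours, and any Arm A versus Arm B total that includes home-visit events, is confounded with ascertainment. As planned, neither a difference nor its absence in those contrasts tests the hypothesis of similar reactions. Comparisons of 30-minute reactions, serious adverse events and the two arms after the 9-month dose are not affected.

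The unequal follow-up is documented; its size is not. On the assumed rates the distortion runs from modest (9% versus 6%, p about 0.18) to enough to produce a clearly significant false difference (9% versus 3%, p about 0.003). Those figures apply to early events only and depend wholly on the assumed true rate and capture. The plan should be changed, but the primary immunogenicity objectives are untouched.

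**What to change.** Replace the adverse event item in the Data Analysis list with four comparisons:

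- **(a)** 30-minute reactions after each dose.
- **(b)** Events reported at the 9-month visit with onset more than 2 days after the enrolment visit, Arm A versus Arm B. Use the onset time on the adverse event form and the same window in both arms. Without the window, Arm A's early events, already reported at home, would drop out while Arm B's stayed in. State open-label recall and Arm A's additional adverse event interview as caveats.
- **(c)** Events after the 9-month dose reported up to the 11-month visit, Arm A versus Arm B.
- **(d)** Serious adverse events by arm.

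Flag every adverse event by source. Report 48-hour events from the home visit as a single-arm incidence for the 6-month dose, and keep them out of all age and arm comparisons. Reword the secondary hypothesis to cover (a) to (d) only.

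The cost is analysis wording and a source flag. The flag should be recoverable, because home-visit findings and visit reports are recorded on different forms. No visits are added; the note on protocol changes in the laboratory section indicates that field data collection is already complete. The price is that the home-visit data become descriptive and early non-serious events are not compared between ages.

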- Identification of immunodeficiency disorder, bleeding disorder or another medical condition for which continued participation, in the opinion of the investigator, would pose a risk to the participant to continue in the study
- Receipt of immunosuppressive medications
- Allergic reaction to a prior dose of measles or rubella containing vaccine or its contents necessitating withdrawal
- Premature termination of the study

- The participant has moved to another area outside of Matlab and is not available for follow up visits
- In case of a withdrawal from study, the local investigator should talk to a parent and document reasons why they are withdrawing, and document any adverse events or conditions that necessitate withdrawal of a participant from the study.

Termination of study

There seem to be no anticipated reasons that may result in suspension or termination of the study.

Nevertheless, there are possible causes that may warrant termination of study:

- Unexpected high number of severe adverse reactions related to use of MR vaccine or any other safety concern then any ethical committee overseeing the study, Ministry of Health or CDC can terminate the study for any safety reasons.
- A large measles or rubella outbreak in the community
- An outbreak response immunization activity with MR vaccine targeting infants aged 6 months and older in the area in response to a large measles or rubella outbreak

Measles or rubella diagnosis; measles or rubella outbreak in the community

If during the course of the study, an infant is diagnosed with a laboratory confirmed measles or rubella infection – it will not be a reason for discontinuation. If an infant is diagnosed with measles or rubella study staff will make sure that the child is non-infectious (at least 4 days after rash onset) then parents will be asked to bring the child to study site for a follow up visit

Concomitant medications and vaccines

- There will be no restrictions on the use of medications or treatments for concomitant diseases. If child is prescribed an immunosuppressive medication then the child will be excluded from the study.
- Parents will be encouraged to get their child vaccinated for other routine childhood vaccines; upon completion of the study, all parents will be reminded to take their child to their assigned vaccination centre to receive a second dose of routine measles vaccine at 15 months of age

Adherence to group assignments

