All serious adverse events will be notified by the principal investigator to the regulatory agencies, ethical review committees and Data Safety Monitoring Board (DSMB) within 24 hours. However, the investigational team will report clusters of AE (at least three within one week) to the DSMB periodically for further evaluation.

Data safety monitoring board (DSMB)

The study will be monitored by a DSMB constituted by icddr,b with input by Ethical Review Committee (ERC). The DSMB will include representation outside of icddr,b. The DSMB is expected to convene once prior to the start of the study after ethical and regulatory approval of study protocol. The DSMB will convene meetings at the time of starting the study, near the middle of the study and at the study completion. The DSMB will be responsible for establishing study stopping rules. Immunogenicity data will not be available for DSMB meetings as all blood specimens will be analysed after the completion of study field activities.

Ethical Assurance for Protection of Human rights

Justification for involving a vulnerable population

Infants will be enrolled at 6 months of age. Enrolment at this early age is required as the study is assessing the immunogenicity of MR vaccine that is recommended at this age during outbreak response activities in response to outbreaks with infants affected at age < 9 months (age for measles routine vaccination). In addition, some researchers have suggested that the first measles vaccination should be given at a time point earlier than 9 months of age, based on the reports that infants born to mothers with vaccine induced immunity against measles may have lower concentrations of maternal antibodies and may lose protection by maternal antibodies at an earlier age.(26, 35, 36) All infants will be administered MR vaccine at age 9 months and some will receive an earlier dose at 6 months. Routine MR second dose will be given at 15 months as per current national immunization schedule endorsed by MoHFW in Bangladesh.

Potential benefits and compensation to participants

Participants will receive all recommended vaccines as per the vaccination schedule of Government of Bangladesh. EPI vaccines will be supplied by the government of Bangladesh. If a child has missed a routine vaccine dose (Pentavalent or polio) that she or he needed to get before the age of 6 months, parents will be encouraged to get their child vaccinated for other routine childhood vaccines.

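### The three-item SAE definition does not require prompt reporting of a grave non-anaphylactic reaction managed without admission, and the defined safety outcome can omit it

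*Combined protocol and SAP*

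**What the plan says.** The combined protocol and SAP deals with serious events in four places.

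- **Recording, monitoring and reporting of adverse events, definition.** "An AE will be considered a serious adverse event if it meets any of the following criteria". The list is "Death during the study period", hospitalization, and "Anaphylaxis associated with vaccine administration". No other section widens it.
- **Same section, reporting.** All SAEs go to regulatory agencies, "ethical review committees and Data Safety Monitoring Board (DSMB) within 24 hours". For other AEs, "the investigational team will report clusters of AE (at least three within one week) to the DSMB periodically for further evaluation". AEs in general are discussed from time to time within the investigator team. The AE form records a description, onset, severity, relationship and resolution.
- **Secondary outcomes, item 2.** Safety has three categories: (a) immediate reactions in the first 30 minutes; (b) AEs in the 48 hours after the 6-month dose; (c) SAEs at any time in the study. Category (c) gives no definition of its own.
- **Termination of study.** One ground is "Unexpected high number of severe adverse reactions related to use of MR vaccine or any other safety concern". The bodies named as able to terminate are the ethics committees, the Ministry of Health and CDC.

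**The concern.** The SAE label does two jobs in this plan: it starts the 24-hour clock, and it decides what enters outcome category (c). The list has no item for a life-threatening event, for lasting disability, or for an event that the investigator judges medically important. Whether a grave reaction other than anaphylaxis counts as serious therefore turns on whether the infant dies or is admitted, not on how grave the reaction was.

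Two things are at stake. The first is prompt outside review of reactions to a live vaccine given three months before the routine age. The second is whether the reported safety outcome for the 6-month dose is complete, since the frequency of adverse reactions after that dose is secondary objective 1.

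**Working it through.** The point rests on a definition and a reporting route, so the main check is to trace one event through the text. Take a grave reaction, not anaphylaxis, 7 to 12 days after the 6-month dose, assessed by a physician and managed without admission.

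| Step | Rule | Result |
|---|---|---|
| SAE list | death, hospitalization, vaccine-associated anaphylaxis | 0 of 3 met |
| 24-hour notice | SAEs only | not required |
| Cluster rule | at least 3 AEs in a week | 1 event: not met alone |
| Outcome (a) | first 30 minutes | outside |
| Outcome (b) | 48 hours after the 6-month dose | outside |
| Outcome (c) | SAEs | outside, by the first row |

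The event is recorded on an AE form and discussed by the investigators. If two other AEs fall in the same week, it can go to the DSMB with them, but without a deadline and not to the ethics committees or regulators.

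**Why days 7 to 12 matter.** The Safety monitoring section puts fever of at least 39.4 °C at 5% to 15% of recipients between days 7 and 12, and rash at about 5% starting on days 7 to 10. Category (b) closes on day 2. With 310 infants in Arm A:

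- high fever: 310 × 0.05 = 15.5 to 310 × 0.15 = 46.5 infants;
- rash: 310 × 0.05 = 15.5 infants.

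These are expected reactions, not grave ones. They show that the systemic reactions the protocol itself anticipates come after both timed categories have closed. From then on only the SAE category remains, and the three-item list alone decides what enters it.

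**How such an event would be noticed.** The home visit is at 2 days and the next scheduled contact is at 9 months, when parents are asked about AEs since the last visit. In between, the route is the parents' own call or visit.

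**Recipients compared.** The 24-hour recipients are regulatory agencies, ethics committees and the DSMB. The bodies that can terminate are ethics committees, the Ministry of Health and CDC. Only the ethics committees are clearly on both lists. The termination ground speaks of severe reactions, a term that is neither defined nor tied to the SAE list, and no severity grade triggers notice.

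**The case against.** The case on the other side has real force on several points.

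**The gap is narrow.** Admission brings an event onto the list, and so does anaphylaxis treated on site. This stands: the point covers only grave non-anaphylactic reactions managed without admission.

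**Other routes exist.** A reader might infer that such an event would never be reported. The documents do not support that. Voluntary notice is not barred, CDC staff review adverse event forms at two monitoring visits, CDC leads the analysis, and the DSMB meets near the middle of the study. None of these routes has a 24-hour clock.

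**The cluster rule is not inert.** A reader might infer that it would hardly ever be met, because grave events are rare. But the rule counts any AEs. Assume about 30 weeks of 6-month dosing (one year, from the Project Summary, less five months of follow-up), a Poisson count per calendar week, and every fever reported as it occurs:

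- 15.5 / 30 = 0.517 per week; P(at least 3) = 0.0157; over 30 weeks, 1 − (1 − 0.0157)^30 ≈ 38%;
- 46.5 / 30 = 1.55 per week; P(at least 3) = 0.204; over 30 weeks ≈ 99.9%.

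So a qualifying week is quite possible from fevers alone. What remains is that the route ends at the DSMB and has no deadline.

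**The alleged contradictions are weaker than they look.** The sentence "Should a serious illness occur while enrolled in the study (requiring a physician's visit or hospitalization), parents will be instructed to seek medical care immediately" might be read as a rival SAE definition. It stands under Safety monitoring and tells parents when to seek care; it defines nothing for reporting. The termination clause also extends to any other safety concern and rests on an aggregate judgement, so it does not depend on single 24-hour notices.

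**The event is not lost from the data.** It is on an AE form, and the analysis section plans a comparison of adverse events by arm and age. It could therefore appear there. It would still be absent from the three defined outcome categories. Nor does the plan rank the SAE category as its main safety result; the three stand side by side.

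**Field work appears to be over.** The assay change under Special Assays or Procedures refers to completed field data collection. A 24-hour clock can no longer help these infants. This stands, and it makes the retrospective step the one that matters.

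**Conclusion.** The concern holds in a limited form. As written, the plan does not require prompt reporting of a grave non-anaphylactic reaction managed without admission. If that reaction falls in the day 7 to 12 window, the defined safety outcome for the 6-month dose can omit it. This follows from the text alone and needs no outside standard.

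Its size can be bounded only loosely. Some 16 to 47 high fevers and about 16 rashes are expected in Arm A after the timed categories close, assuming that the protocol's general rates apply at 6 months of age. How many graver events would arise is unknown: the documents give no rate for them, and the count may be zero. The point is a cheap improvement to the completeness of the safety results, not evidence that any event was missed.

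**What to change.** 1. Widen the SAE list to include life-threatening events, persistent disability, and events that the investigator judges medically important, whether or not the infant was admitted.
2. Reconcile the wording of Termination of study, safety outcome category (c) and the 24-hour rule with that list. State how severe reactions in the termination clause relate to SAEs, and which bodies receive notice.
3. Because field data collection appears complete, re-screen the completed AE forms against the wider list. The forms already provide for description, onset, severity and relationship. Report any event found to the recipients named in the 24-hour rule and include it in the SAE results.
4. Declare in the report that this reclassification was made after data collection, and give the SAE count under both the three-item list and the wider list.

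The cost is protocol wording and some review of existing forms, with no new visits or samples. The SAE count may rise slightly. A definition changed after data collection invites the question of why it was changed, which the declaration and the two counts answer.
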